9.1.2 Events Not to be Considered as Adverse Events

A pre-existing condition (i.e., a disorder that is present before the AE recording period starts and is noted on the medical history/physical examination form) should not be recorded as an AE unless the condition worsens, or episodes increase in frequency during the AE recording period. Refer to **Section 9.2.1**

PD will not be captured as an AE unless the nature of the PD is different than expected (i.e., signs/symptoms that are not typical of PD).

Note: PD may be reported as an AE in the case of patient death, with death being the outcome of the event.

An abnormal laboratory value or an abnormality in physiological testing (such as ECGs) per se need not be reported as an AE unless one of the following applies:

- The Investigator considers the abnormality clinically significant
- The event meets the definition of an SAE
- The event requires an intervention
- The event results in an action taken with Pan-HER (dose-reduction and/or withdrawal)

Diagnostic and therapeutic non-invasive and invasive procedures, such as surgery, should not be recorded as AEs. A medical condition for which an unscheduled procedure was performed, should however be recorded if it meets the definition of an AE. For example, an acute appendicitis should be recorded as the AE and not the appendectomy.

Confidential Page 86 of 156

Procedures to support the treatment regimens, such as insertion of central venous catheters etc. should not be recorded as AEs, unless the procedures result in complications.

9.1.3 Adverse Events of Medical Interest

Not applicable.

9.1.4 Serious Adverse Events

An SAE is an AE that meets one or more of the following regulatory outcomes criteria:

• Results in death

Note: In the case of deaths, the event(s) leading to the death should be recorded and reported as SAE(s) with the outcome "Fatal". The death itself will not be reported as an event (SAE), unless the cause of the death is unknown (e.g., in case of unexplained or sudden death).

• Is life-threatening

Note: The term "life-threatening" in this definition refers to an event in which the patient is at immediate risk of death at the time of the event; it does not refer to an event which hypothetically might cause death if it was more severe.

- Requires inpatient hospitalization or prolongation of existing hospitalization
- Results in persistent or significant disability/incapacity
- Is a congenital anomaly/birth defect
- Is medically important

Note: Medical and scientific judgment must be exercised in deciding whether an AE is believed to be "medically important". Medically important events may not be immediately life-threatening or result in death or hospitalization but may jeopardize the patient or may require intervention to prevent one of the other outcomes listed in the definition above.

9.1.5 Events that Do Not Meet the Definition of Serious Adverse Events

PD will not be captured as an SAE unless the nature of the PD is different than expected (i.e., signs/symptoms that are not typical of PD).

Note: PD may be reported as an SAE in the case of patient death, with death being the outcome of the event.

Elective surgery or other scheduled hospitalization periods that were planned before the patient was included in this trial are not to be recorded as SAEs, unless an outcome is considered serious.

Confidential Page 87 of 156

Hospitalization for observation or convenience following the Pan-HER infusions without an SAE occurring should not be recorded as an SAE, e.g., if a patient is hospitalized merely for observation, or if a patient finalizes the infusion at a time of day requiring a convenience overnight stay in the hospital.

If procedures to support the treatment regimens require hospitalization, they should not be recorded as SAEs. However, in cases where a procedure results in complications requiring/prolonging hospitalization this must be recorded and reported as an SAE.

9.2 Adverse Event Recording and Reporting Instructions

9.2.1 Adverse Event Recording Period

All AEs will be recorded from signing of informed consent for participation in the trial. The recording period ends at the time of the 1M FUP Visit.

Note: Patients who sign informed consent and are subsequently deemed to be screening failures will be followed for the occurrence of SAEs/AEs until it is determined that they will not be participating in the trial.

The Investigator must record all directly observed AEs and all AEs spontaneously reported by the patient. A general, open-ended type of question should be used to elicit a response from the patient, such as, "How have you been feeling?" or "Have you had any health problems since your last visit?".

All AEs that occur in patients during the AE recording period must be recorded/entered on the AE section of the Case Report Form (CRF), whether or not the event is assessed as related to Pan-HER. If the AE is serious, the SAE report forms must also be completed and submitted (see **Section 9.3**).

9.2.2 Diagnosis

A diagnosis should be recorded if possible. If no diagnosis is available, signs and symptoms should be recorded instead.

9.2.3 Intensity

All referenced toxicity grading within this protocol will be according to the CTCAE v4.03. If the severity of an AE is not specifically graded by the CTCAE guidance document, the Investigator should use the general definitions of Grades 1 to 5 as per the following, and use his/her best medical judgment to describe the severity of the AE:

• Grade 1: Mild

Confidential Page 88 of 156

- Grade 2: Moderate
- Grade 3: Severe
- Grade 4: Life-threatening or disabling
- Grade 5: Death caused by the event

Changes in severity of AEs will be recorded.

Generally, an AE of Grade 4 or 5 qualifies for SAE reporting to the Sponsor or designee; however, the definition of Grade 4 does not necessarily always meet the regulatory definition of "life-threatening". As an example, a laboratory abnormality of Grade 4 does not need to be reported as an SAE, unless it meets one of the seriousness criteria in **Section 9.1.4**.

9.2.4 Relationship to Investigational Medicinal Product/Pan-HER

The Investigator must assess causal relationship to the IMP, Pan-HER. Relatedness has to be assessed and recorded within the initial report (CRF and SAE report form).

The causal relationship is an assessment of whether or not the event is related to the use of the IMP. It is not an evaluation of whether or not the event could hypothetically occur in the investigational patient population.

The causal relationship of an AE to the IMP, Pan-HER, will be rated as follows:

Not Related: The AE is not related to the IMP, which means the event:

- Does not follow a reasonable temporal sequence from drug administration
- Is readily explained by the patient's clinical state or by other modes of therapy administered to the patient
- The AE is clearly NOT related to the IMP

Unlikely Related: The AE is considered not related to the IMP based on the following:

- Does not follow a reasonable temporal sequence from administration of drug
- Could readily be a result of the patient's clinical state, environmental, or toxic factors, or other modes of therapy
- Does not follow a known response pattern to the suspected drug
- Does not reappear or worsen when the drug is re-administered

Confidential Page 89 of 156

Possibly Related: The AE might not be related, but possibility cannot be ruled out with certainty and therefore would be considered related based on:

- Follows a reasonable temporal sequence from administration of drug
- Could readily have been a result of the patient's clinical state, environmental or toxic factors, or other modes of therapy
- Follows a known response pattern to the suspected drug

Probably Related: It has been determined with a high degree of certainty that the AE is associated with administration of IMP based on:

- Follows a reasonable, temporal sequence
- Cannot be reasonably explained by known characteristics of the patient's clinical state, environmental, or toxic factors, or other modes of administered therapy
- The AE disappears or decreases in severity upon cessation of drug, or reduction in dose.
- Follows a known response pattern to the suspected drug

Related: The AE is related to the IMP, which means the event:

- Follows a reasonable temporal sequence from drug administration
- Abates upon discontinuation of the IMP (de-challenge)
- Is confirmed by reappearance of the reaction on repeat exposure (re-challenge)
- Cannot be reasonably explained by the known characteristics of the patient's clinical state
- Is not likely to have been produced by the patient's clinical state or by other modes of therapy administered to the patient

9.2.5 Outcome

Outcome of the AE must be assessed by the Investigator utilizing one of the following terms:

- Recovered
- Recovered with sequelae (if recovered with sequelae, specify sequelae)
- Not recovered
- Fatal
- Unknown

Instructions for reporting changes in an ongoing AE during a patient's participation in the trial are provided in the instructions that accompany the AE CRF pages.

Confidential Page 90 of 156

9.2.6 Follow-up of Adverse Events

All AEs should be followed until resolution or until the 1M FUP Visit, whichever comes first.

Note: Patients who sign informed consent and are subsequently deemed to be screening failures will be followed for the occurrence of SAEs/AEs until it is determined that they will not be participating in the trial.

9.3 Serious Adverse Event Recording and Reporting

9.3.1 Timeframes for Reporting to the Sponsor

All SAEs occurring at any time from signing of informed consent for participation in the trial and until the 1M FUP Visit must be recorded on the SAE Report Form and recorded as an SAE in the CRF.

Note: Patients who sign informed consent and are subsequently deemed to be screening failures will be followed for the occurrence of SAEs/AEs until it is determined that they will not be participating in the trial.

In case of an SAE, the Investigator must, within 24 hours of first awareness of the event, report the SAE to the Sponsor or designee by fax or e-mail transmission. Fax number(s) and e-mail address(es) will be stated on the SAE Report Form and the SAE Report Form Completion Instructions. SAE follow-up information must also be reported to the Sponsor or designee within 24 hours of awareness.

SAEs still ongoing after the 1M FUP Visit should be followed on a regular basis according to the Investigator's clinical judgment, until the event has been resolved or until the Investigator assesses it as chronic or stable. The Sponsor or designee will pursue sufficient information and will return to the trial sites for such information as deemed required.

If the Investigator becomes aware of an SAE that occurred after the 1M FUP Visit and finds it to be related to the IMP (possibly-, probably-, or related to Pan-HER) or trial conduct, it must be recorded and reported to the Sponsor or designee as an SAE. These SAEs considered related to the IMP and occurring after the 1M FUP Visit will not be reported in the CRF but only on an SAE Report Form instead for recording in the safety database.

The Investigator should be aware of local reporting regulations to the Institutional Review Board (IRB)/Ethics Committee (EC). The Sponsor or designee will either supply the Investigator with the reports, which should be forwarded to the IRB/EC, or report directly to the IRB/EC depending on local regulations.

Confidential Page 91 of 156

9.4 Safety Reporting to Health Authorities, Institutional Review Boards/Ethics Committees, and Investigators

Reportability of an SAE as a "Suspected Unexpected Serious Adverse Reaction" (SUSAR) will be determined solely by the Sponsor, based on seriousness, causality, and expectedness criteria.

In addition to SUSARs, the Sponsor or designee is responsible for reporting all relevant safety information regarding SUSARs, or other safety developments, to appropriate HAs and central IRBs/ECs, as well as participating investigators. Reporting of SUSARs to local IRBs/ECs will be handled by the Investigator.

The timeline for notification of SUSARs is within 7 calendar days for fatal/life-threatening events and within 15 calendar days for all other SUSARs.

Additionally, the annual Development Safety Update Report (DSUR) will be submitted by the Sponsor or designee to all appropriate HAs and central IRBs/ECs as per ICH Guidelines. Submission of the DSUR to local IRBs/ECs will be handled as per local regulations and/or requests.

9.5 Dose-Limiting Toxicities (Part 1 Only)

9.5.1 Definition of Dose-Limiting Toxicities

A DLT is defined as any of the following toxicities that occur during the DLT-observation period, if considered related (causality rating of possibly, probably, or related) to Pan-HER:

- 1. Grade 3 non-hematologic toxicity regardless of duration, with the exception of:
 - a. Grade 3 nausea, vomiting, diarrhea, or fatigue lasting ≤2 days with best supportive care
 - b. Grade 3 asymptomatic electrolyte abnormality that is not considered clinically significant by the Investigator and that is controlled with medical therapy
- 2. Grade 4 non-hematologic toxicity, with the exception of:
 - a. Grade 4 asymptomatic electrolyte abnormalities that is not considered clinically significant by the Investigator and that is controlled with medical therapy
- 3. Neutropenia that is:
 - a. Grade 3-4 febrile neutropenia
 - b. Grade 4 and sustained (i.e., ANC $< 0.5 \times 10^9 / L [500 / mm^3]$, duration > 5 days)
- 4. Thrombocytopenia that is
 - a. Grade 3 with clinically significant hemorrhage

Confidential Page 92 of 156

- b. Grade 4 (platelets $<25 \times 10^9/L [25,000/mm^3]$)
- 5. AST/ALT elevation >3×ULN with bilirubin elevation >2×ULN without evidence of cholestasis that cannot be explained by factors not related to Pan-HER
- 6. Evidence of cardiac toxicity as defined by either:
 - a. ≥16% absolute decrease in LVEF from baseline, or
 - b. LVEF below the institutional lower limit of normal and ≥10% absolute decrease in LVEF from baseline
- 7. Inability to complete Cycle 1 at the assigned dose due to \geq Grade 3 toxicity
- 8. Treatment delays >2 weeks from the scheduled next dose due to \ge Grade 3 toxicity

9.5.2 Observation Period for Dose-Limiting Toxicities

The decision to dose-escalate will be based on close monitoring of safety during the observation period for DLTs, defined as the initial 28-day period (±2 days) from first treatment of Pan-HER (i.e., Cycle 1) and including 7 days of follow-up (Q1W dosing) or 14 days of follow-up (Q2W dosing) from the last dose of Cycle 1.

A minimum of 4 Pan-HER infusions (Q1W dosing) or 2 Pan-HER infusions (Q2W dosing) must have been administered at the assigned dose for a patient to have completed the DLT-observation period.

9.5.3 Reporting of Dose-Limiting Toxicities

All presumed DLTs must be reported to the Sponsor or designee within 24 hours after the Investigator or designee have become aware of the event. In addition, DLTs fulfilling the SAE criteria must be reported according to the procedure for SAEs, as outlined in **Section 9.3**.

9.6 Reporting of Infusion-Related Reactions

The definition of an IRR is included in **Section 7.1.3.6**.

All IRRs must be reported in the CRF as an AE with the term "Infusion-related Reaction" followed by a specification of symptoms (e.g., "Infusion-related Reaction with dyspnea and flushing").

To facilitate ongoing safety review throughout the course of this trial, the occurrence of \geq Grade 2 IRRs must be reported to the Sponsor or designee within 24 hours of occurrence. As always, any IRR fulfilling the SAE criteria must be reported as per **Section 9.3**.

Confidential Page 93 of 156

9.7 Pregnancy

If any trial patient becomes pregnant during the course of the trial, the patient must be discontinued from Pan-HER immediately and the pregnancy must be reported to the Sponsor or designee according to the same timelines as for an SAE. While pregnancy is not considered an AE, all pregnancies are tracked as SAEs within the safety database in order to follow-up on exposure to the fetus/infant.

Pregnancies reported in female partners of male trial patients must also be included in the safety database; therefore, a female partner of a male patient on the trial who becomes pregnant will be approached for consent to have the pregnancy followed until term and reported upon to the Sponsor or designee.

All pregnancies must be followed up every third month to determine outcome and status of mother and child. Pregnancy complications and elective terminations for medical reasons must be reported as AEs or SAEs as appropriate. Elective terminations for non-medical reasons should be reported as follow-up, but not as a separate AE/SAE unless complications meet AE/SAE criteria. Spontaneous abortion must be reported as an SAE.

Any SAE occurring in association with a pregnancy brought to the Investigator's attention after the patient has completed the trial and considered by the Investigator as possibly-, probably-, or related to Pan-HER must be promptly reported to the Sponsor or designee.

All pregnancy information including follow-up information must be reported on a designated pregnancy form provided by the Sponsor or designee.

Confidential Page 94 of 156

10. STATISTICS

10.1 Sample Size Considerations

The primary endpoint of Part 1 is occurrence of DLTs during Cycle 1 for each of the Pan-HER dosing regimens. The number of enrolled patients will depend on the extent of observed DLTs independently in each cohort. Please refer to **Section 7.1.3.2** for a description of planned dose levels and decision points for dose-escalation. Based on the dose-escalation design, it is planned to enroll approximately 34 patients during the dose-escalation part of the trial.

In Part 2 of the trial, the primary endpoint is documented OR, defined as documented PR or CR assessed by RECIST v1.1 at any time during trial participation, with radiologic evaluation to be performed locally.

During Part 2, it is planned to enroll and treat approximately 100 patients. The planned number of patients to be enrolled might be adjusted when the 4 dose-expansion cohorts (i.e., based on defined molecular profiles(s) and tumor types) have been selected. The protocol amendment defining the dose-expansion cohorts will contain a detailed sample size calculation covering the four expansion cohorts, including expected range of OR.

10.2 Analysis Population

Two analysis sets will be defined in accordance with the consolidated ICH E9 GCP guidelines.

The Full Analysis Set (FAS) will comprise all enrolled patients who have received at least one dose of Pan-HER. The FAS will be used for evaluation of all endpoints except evaluation of DLTs. The patients in the FAS will contribute to the analyses as allocated to treatment. For the evaluation of PK endpoints, patients, full profiles, or single measurements can be excluded from the analyses. The decision of excluding patients, full profiles, or part of profiles will be described in the clinical trial report (CTR).

The DLT Analysis Set will comprise all patients in the FAS enrolled in Part 1, except patients who did not complete Cycle 1 for reasons other than drug toxicity. The DLT Analysis Set will be used for evaluation of DLTs.

Confidential Page 95 of 156

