6.4 Replacement of Patients

6.4.1 Part 1, Dose-Escalation Cohorts

Patients in Part 1, who do not complete Cycle 1 as defined in **Section 9.5.2**, for reasons other than drug toxicity, will be replaced.

Data from these patients will be included in the safety analysis, but will not contribute to the determination of the MTD.

Confidential Page 53 of 156

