4.5 Analysis Sets

Two analysis sets will be defined in accordance with the consolidated ICH E9 GCP guidelines.

The Full Analysis Set (FAS) will comprise all enrolled patients who have received at least one dose of Pan-HER. The FAS will be used for evaluation of all endpoints except evaluation of DLTs. The patients in the FAS will contribute to the analyses as allocated to treatment (patients will be reported below the regimen and dosage actually received). For the evaluation of PK endpoints, patients, full profiles, or single measurements can be excluded from the analyses with justification. The decision of excluding patients, full profiles, or part of profiles will be described in the clinical trial report (CTR).

The DLT Analysis Set will comprise all patients in the FAS enrolled in Part 1, except patients who did not complete Cycle 1 for reasons other than drug toxicity. The DLT Analysis Set will be used for evaluation of DLTs and the MTD or lack thereof.

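### A patient with a DLT whose recorded reason for not completing Cycle 1 is something other than toxicity is replaced and leaves the MTD count and the DLT outputs

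*Protocol*

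**What the plan says.** - **Analysis set.** Protocol 10.2 takes all Part 1 patients in the FAS "except patients who did not complete Cycle 1 for reasons other than drug toxicity", and states: "The DLT Analysis Set will be used for evaluation of DLTs". SAP 4.5 repeats the definition and widens its use: "The DLT Analysis Set will be used for evaluation of DLTs and the MTD or lack thereof".
- **Replacement.** Under protocol 6.4.1, patients who do not complete Cycle 1, as defined in 9.5.2, "for reasons other than drug toxicity, will be replaced". It adds: "Data from these patients will be included in the safety analysis, but will not contribute to the determination of the MTD".
- **Completion.** Protocol 9.5.2 sets a 28-day observation period with 7 days (Q1W) or 14 days (Q2W) of follow-up after the last Cycle 1 dose. At least 4 (Q1W) or 2 (Q2W) infusions "must have been administered at the assigned dose for a patient to have completed the DLT-observation period".
- **DLT item 7.** Protocol 9.5.1 makes "Inability to complete Cycle 1 at the assigned dose due to" toxicity of Grade 3 or higher a DLT in its own right.
- **Escalation.** In protocol 7.1.3.2, the zero-DLT rule counts the first 3 patients to complete Cycle 1. The rules for 1 of 3 and for 2 or more DLTs count patients at the dose level, with no completion condition.
- **Outputs.** Protocol 10.3.1 and SAP 4.11.1 say every DLT event will be listed. In SAP section 6, Table 14.2.4.8 and Listing 16.2.7.1 are restricted to the DLT set.

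**The concern.** Both set membership and replacement depend on why Cycle 1 was not completed. Neither depends on whether the primary endpoint event was seen. A DLT is conclusive once it has occurred: the patient needs no further follow-up to be informative. Even so, no clause in 6.4.1, 10.2 or SAP 4.5 keeps that patient in.

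Take a patient who receives every Cycle 1 infusion at the assigned dose, has a DLT in the follow-up after the last one, and withdraws consent or progresses before that follow-up ends. The recorded reason is not toxicity. Read literally, the patient is replaced and the DLT goes uncounted.

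Occurrence of DLTs in Cycle 1 is the Part 1 primary endpoint, and in a 3+3 design a single patient decides the outcome at a dose level. The documents also disagree with each other on this patient. The 7.1.3.2 rules for 1 of 3 and for 2 or more DLTs would count the event, while 6.4.1 says the data are not to count. A listing of every DLT cannot be complete if it is drawn from a set that can exclude one.

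**Working it through.** **1. The plan's own rule.** Protocol 10.3.1 and 7.1.3.2 accept at most 1 DLT in 6 patients. Two or more means the MTD is exceeded. 1/6 = 16.7% and 2/6 = 33.3%, which agrees with the target of below 33% in protocol 5.1.

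**2. One affected patient.** Six patients are treated and two have a DLT: 2/6, MTD exceeded. One of the two is recorded as leaving for another reason and is replaced by a patient without a DLT. Five original patients plus one replacement now carry one DLT: 1/6, MTD confirmed. In the same way 1/3 (expand to 6) becomes 0/3 (escalate).

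**3. Which patients fall in the gap.**
- Protocol 7.1.4.3 requires dose reduction for a list that matches DLT items 1 to 6, apart from one baseline clause for AST/ALT. Protocol 7.1.4.2 bars redosing while an event meets DLT criteria. A patient with a DLT early in Cycle 1 therefore cannot receive the remaining infusions at the assigned dose, and the cause is toxicity. That patient stays in the set, and item 7 points the same way.
- Two cases remain: (a) the site records only a later reason such as consent withdrawal or PD, and (b) the DLT follows the last Cycle 1 infusion and the patient departs during the 7- or 14-day follow-up. Case (b) assumes that such a departure counts as not completing the period.
- Protocol 3.2.4.1 reports two DLTs, both at 9 mg/kg Q2W. One patient was discontinued after a Grade 3 IRR. The other had Grade 3 mucositis and was retreated at a reduced dose. Both stay in the set.

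**4. Hypothetical worst case.** Let p be the true DLT rate, q the share of DLT patients who leave this way, and c the share of DLT-free patients who leave and are replaced. The documents give neither q nor c. As written, the counted rate is

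p′ = p(1 − q) / [p(1 − q) + (1 − p)(1 − c)]

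and the 3+3 probability of escalating is (1 − p′)³ + 3p′(1 − p′)⁵.

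For p = 0.40, q = 0.10, c = 0: p′ = 0.36/0.96 = 0.375, and 0.625³ + 3 × 0.375 × 0.625⁵ = 0.244 + 0.107 = 0.351. With c = 0 throughout:

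| q | p′ (p = 0.40) | P(escalate) | p′ (p = 0.33) | P(escalate) |
|---|---|---|---|---|
| 0 | 0.400 | 30.9% | 0.330 | 43.4% |
| 0.10 | 0.375 | 35.1% | 0.307 | 48.0% |
| 0.20 | 0.348 | 40.1% | 0.283 | 53.0% |
| 0.30 | 0.318 | 45.8% | 0.256 | 58.6% |

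**5. Equal leaving in both groups.** With c = q the factor cancels and p′ = p. For p = 0.40 and q = c = 0.10: 0.36/(0.36 + 0.54) = 0.40. The expected counted rate is unchanged, although an observed DLT is still discarded from the particular cohort where it occurred.

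**The case against.** The strongest defence is that the protocol's other rules already hold on to nearly every DLT patient. Mandatory dose reduction, the bar on redosing, the assigned-dose condition and item 7 together make non-completion after an early DLT a matter of toxicity. That stands, and it reduces the problem to the two residual cases in the working.

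A second defence is that the SMC decides escalation from all safety data, that DLTs must be reported within 24 hours, and that two of the 7.1.3.2 rules count patients at the dose level without any filter. This is fair, but those rules contradict 6.4.1 and do not override it. The 7.1.3.2 note on additional patients covers extra patients entered to a cohort, not a patient who has been replaced. Under SAP 4.4.2, analysis-set assignment is decided at the data review meeting, but nothing there says that a patient with a DLT must be kept.

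Third, enrolment stopped in Part 1, Part 2 never opened, and the analysis is descriptive. This limits the consequence to how the DLT result and the MTD conclusion are reported.

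A reader might also infer that patients who miss Cycle 1 infusions because of toxicity below Grade 3 drive escalation, since they remain in the set as DLT-free. The documents do not support that. After zero DLTs, 7.1.3.2 needs three patients who complete Cycle 1, and dosing at the next level waits for completion at the current one. Such patients affect only the denominator of the reported DLT rate, where keeping or excluding them is a debatable choice.

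**Conclusion.** The omission is real and follows from the wording of 6.4.1, 10.2 and SAP 4.5. It is narrow, and its severity is minor to moderate. One affected patient is enough to reverse a cohort decision from 2/6 to 1/6. That conclusion needs only the replacement to be DLT-free.

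The escalation percentages are weaker evidence. They assume values of q that the documents do not give, and that no DLT-free patient leaves. They show a worst case, not an expected effect.

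A reader might infer that DLT rates in this trial are systematically understated, or that DLT events disappear from reporting. Neither is supported. With equal leaving rates there is no bias in the expected rate, and the documents report no such case. The event also stays in the FAS adverse event summaries and in the all-consented adverse event listing. The documents give no DLT outcomes after Amendment 6, so whether a later patient is affected cannot be settled from them.

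**What to change.** - **Protocol 10.2 and SAP 4.5:** add that any Part 1 FAS patient with a DLT in the observation period is always in the DLT Analysis Set, whatever the recorded reason for not completing Cycle 1.
- **Protocol 6.4.1:** limit replacement, and the bar on contributing to the MTD, to patients without a DLT. Reconcile the section with the counting rules in 7.1.3.2.
- **Outputs:** Table 14.2.4.8 and Listing 16.2.7.1 then cover every DLT, as 10.3.1 and SAP 4.11.1 say they should.
- **Optional:** flag in the DLT listing any patient kept in the set without a DLT who did not receive the infusions required by 9.5.2.

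The cost is about one sentence per section and no new data. With enrolment stopped, the SAP sentence matters most and should be in place before database lock.

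The change also moves the counted rate upward when DLT-free leavers are replaced. With p = 0.40 and 10% of DLT-free patients leaving, the counted rate is 0.40/(0.40 + 0.60 × 0.90) = 42.6%, and the chance of escalating is 26.9% instead of 30.9%. That error is on the cautious side.
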